#### **6.4.4 Hazard ratios**

Hazard Ratios will be derived for the main endpoints from Cox proportional hazard model with treatment group as an independent variable. Other covariates could include, but are not limited to age, BMI, race, hormonal contraception used at baseline and appropriate pre-existing conditions (bleeding disorder, ovarian pathology, etc.).

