5.1 Design overview

Section modified by Amendment 2 ([Modification 2](#))

This will be an open-label, non-randomized, continuous enrollment, prospective observational postmarket surveillance study of two cohorts of subjects who chose to undergo:

- hysteroscopic sterilization (Essure System), or
- laparoscopic tubal sterilization.

The targeted number of sites for participation in the study is up to 90.

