5.2 Endpoints and variables

5.2.1 Main endpoints

Section modified by Amendment 1 (Section [16.1](#)) and Amendment 2 ([Modification 3](#), [Modification 4](#), [Modification 5](#), [Modification 7](#)).

- **Pain:** The proportion of subjects reporting AEs of chronic lower abdominal and / or pelvic pain after insertion of Essure System compared to the proportion of subjects reporting AEs of chronic lower abdominal and / or pelvic pain after laparoscopic tubal sterilization. Total incidence of pain events will be based on AE reporting. If a potential pain event is spontaneously reported outside of a scheduled visit or scheduled patient-reported outcome (PRO) tool administration, the pain PRO tools (Patient-Reported Outcomes Measurement Information System [PROMIS] Scale V1.0 – Pain Intensity 3a and PROMIS Scale V1.0 – Pain Interference 8a Participant Format; see Section [9.2.3](#)) will be administered off-schedule in order to characterize pain intensity and interference. If during the course of a scheduled PRO administration (see [Table 9–2](#) and Section [9.2.3](#)) the subject reaches a preset threshold for pain on a PRO tool, even if she has not spontaneously reported a pain event to the investigator, the investigator will be alerted and instructed to investigate this finding in order to determine whether or not an AE has occurred. Standard criteria for AE assessment (e.g., new or worsening symptom) will be used and all investigators will be trained on standard AE assessment.

The preset thresholds that will trigger investigation of pain as an AE are as follows: on the PROMIS Pain Intensity Scale, a score of 3 (moderate intensity) for the ‘pain at its worst’ question will trigger investigation regardless of the other scores or results of the PROMIS Pain Interference Scale. For PROMIS Pain Interference Scale, a t-score of ≥ 60 (which corresponds to a raw score of ≥ 22) or any single item raw score of ≥ 4 will trigger investigation regardless of the results of the PROMIS Pain Intensity Scale. Section [9.2.3](#) includes justification for these thresholds. Not all reports of pain that are reported on the PRO tool will be considered AEs. This is particularly notable in the case of a subject who has pre-existing pain that continues to be unchanged post-sterilization procedure.

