6.1 Inclusion criteria

Section modified by Amendment 2 (Modification 8, Modification 9).

1. Signed and dated informed consent;
2. Subjects who are at least 21 years of age;
3. Subjects of all weights will be included;
4. Subjects who are scheduled to undergo an Essure insert placement procedure for permanent birth control or laparoscopic tubal sterilization. Decision for either treatment based upon clinical practice and physician / patient counseling;

5. For the Essure group only:
 - Subjects selecting hysteroscopic sterilization who are not contraindicated for the Essure procedure according to the most current approved version of the Essure IFU;
 - Subjects must have received the most current approved version of the Patient Information Booklet (PIB) and completed the Essure patient checklist;
 - Subjects selecting Essure who are willing to use alternative contraception for at least 3 months post-Essure placement procedure, until a satisfactory Essure Confirmation Test is documented;
 - Subjects who are believed to have two viable fallopian tubes.
6. For the laparoscopic tubal sterilization group only:
 - Subjects selecting laparoscopic sterilization who are not contraindicated for laparoscopic tubal sterilization according to common clinical practice standard of care;
 - After signed informed consent, subjects must have received the American College of Obstetricians and Gynecologists (ACOG) Patient Information Brochure on Sterilization by Laparoscopy and completed the laparoscopic tubal sterilization patient checklist.
7. Subjects who are willing to accept the risk of pregnancy occurring while relying on the Essure device or laparoscopic tubal sterilization for prevention of pregnancy;
8. Subjects who have the capacity to understand the informed consent, comply with the protocol requirements, and provide reliable feedback during the follow-up period;
9. Subjects who agree to participate in the scheduled study visits;
10. Subjects who are willing to allow data to be shared with the sponsor and with regulatory bodies.

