## **4 General statistical considerations**

All issues concerning subject validity, data consistency checks, as well as coding of medical terms and concomitant medication will be described in detail in the Data Management Plan. All statistical issues including calculated variables are detailed in this Statistical Analysis Plan.

The study is observational and does not allow a randomized decision for treatment allocation. Therefore, the allocation of procedure to a subject is driven by preferences, medical decision, medical circumstances and other information the treating physician requires for the selection of the best option. Allocation bias must therefore be assumed, with consequent potential for confounding. Under such conditions, formal statistical hypotheses of no treatment effect would include an unknown size of bias, as the size of the confounding remains unknown a priori. In particular, the confounding may nullify differences between groups, due to the size of the confounding that cannot be attenuated through analytical methods, but also may inflate differences.

Attempts can be made by analytical procedures to adjust for measured confounding, but still, in this setting, unmeasured confounding cannot be quantified. Several scenarios of analyses are therefore planned to be employed, addressing several of these sources of confounding.

It is expected that, due to the media attention given to the Essure procedure, there will be significant confounding between the 2 treatment groups leading to channeling bias that will be insurmountable with any analytical method.

The analysis must therefore be considered exploratory in nature.

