## 6 Statistical methodology

### 6.1 Population characteristics

#### 6.1.1 Background data

The numbers of subjects enrolled and included in the analysis populations will be tabulated by site. The reasons for subjects excluded from the analysis populations will also be tabulated.

The descriptive analysis will be performed for the baseline variables. All background data such as subject demographics, medical history, index event, risk factors, concomitant diseases and conditions as well as concomitant medication will be described by presenting frequencies and/or summary statistics. [Table 1](#) lists baseline variables to be presented for descriptive analysis. Tables on prior medication, concomitant medication will show frequencies using the WHO Drug Dictionary Version Q1 2016, or later if updated during the study, and the Anatomical Therapeutic Chemical (ATC) Classification codes.

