#### **6.4.1 Subject Incidence**

The subject incidence is defined as the number of subjects with at least one event divided by the number of subjects at risk. Subject incidence will be calculated for each group. The risk difference between two groups will also be calculated. Its associated 95% CI will be derived based on normal approximation.

Additionally for the main endpoints, subject incidence and risk differences will be given for the following time intervals: Day 0, Day 1-7, Day 8-30, Day 31-90, Day 91-180, Day 181-365, Day 366-730, > Day 730.

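### The stated between-arm intervals ignore site, so they are too narrow if procedure choice and outcome recording both cluster by site

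*SAP*

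**What the plan says.** Protocol 5.1 sets the scale: "The targeted number of sites for participation in the study is up to 90". Procedure is not randomised. Protocol 6.1 puts it this way: "Decision for either treatment based upon clinical practice and physician / patient counseling". SAP 4 adds that "the allocation of procedure to a subject is driven by preferences, medical decision, medical circumstances and other information the treating physician requires".

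For pain, when a questionnaire threshold is reached, Protocol 5.2.1 says that "the investigator will be alerted and instructed to investigate this finding in order to determine whether or not an AE has occurred". The bleeding endpoint is handled in the same way.

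For the main endpoints the SAP plans three between-arm contrasts:

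- **Risk difference (6.4.1):** "The risk difference between two groups will also be calculated", with a 95% interval from a normal approximation.
- **Difference in exposure-adjusted incidence (6.4.2):** a 95% interval from a cited published method.
- **Hazard ratio (6.4.4):** "Hazard Ratios will be derived for the main endpoints from Cox proportional hazard model with treatment group as an independent variable". An open list of patient covariates follows. No interval, p-value or variance estimator is given.

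In the SAP's analysis text, site is used once, in 6.1.1: "The numbers of subjects enrolled and included in the analysis populations will be tabulated by site". Table 5 (propensity-score candidates) has geographical region. Table 1 has physician experience with each procedure, specialty and facility or setting. Neither table has a site identifier. The 1:1 matching in 6.6.1 is not restricted to pairs within a site. Neither document mentions site stratification, frailty, a random site effect or cluster-robust variance.

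**The concern.** Women treated at one site share operators, counselling habits and an investigator who decides what becomes an adverse event. If sites also differ in which procedure they mostly perform, a site's recording habits fall largely on one arm. The effective number of independent observations is then smaller than the number of women, and an interval computed as if women were independent is too short.

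Interval width matters here because no confirmatory test is planned. The intervals and p-values are the plan's means of expressing uncertainty in a study that a regulator required. A false signal, or false reassurance about precision, on pain or bleeding would be hard to correct afterwards. Matching does not settle the matter, because pairs can be formed across sites.

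**Working it through.** The plan states no sample size, event rate or power, so it has no figure to reproduce. The only numeric anchor is the two-sided 95% level, z = 1.96.

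**Inputs from the documents:** up to 90 sites (Protocol 5.1); about 2:1 laparoscopic to Essure (SAP 4.1).

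**Assumptions:** 400 to 1500 women; 50 to 90 contributing sites; coefficient of variation of site size cv = 0.8; outcome ICC ρy from 0 to 0.10; ICC of procedure choice ρx from 0 (same mix everywhere) to 1 (one procedure per site). Below, 0.3 is called moderate concentration and 0.6 or more strong.

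**Step 1: variance inflation.** With m women per site on average,

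DE = 1 + (m(1 + cv²) − 1) × ρy × ρx, and coverage = 2Φ(1.96/√DE) − 1.

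For 900 women at 90 sites, m = 10 and m(1 + 0.64) − 1 = 15.4. At ρy = 0.05:

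- ρx = 0: DE = 1, coverage 0.950
- ρx = 0.3: DE = 1 + 15.4 × 0.05 × 0.3 = 1.23, coverage 0.923
- ρx = 0.6: DE = 1.46, coverage 0.895
- ρx = 1.0: DE = 1.77, coverage 0.859

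The corners of the range, both at ρx = 1:

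- 400 women, 90 sites, ρy = 0.01: m = 4.44, DE = 1.06, coverage 0.943.
- 1500 women, 50 sites, ρy = 0.10: m = 30, DE = 1 + 48.2 × 0.10 = 5.82, coverage 0.58.

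**Step 2: simulation of the 6.4.1 interval.** True difference 0, event risk 10%, 2:1 allocation, 900 women, ρy = 0.05, 2000 runs per cell. The SE ratio is clustered over planned.

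| ρx | 90 sites, planned | 90 sites, site-clustered | SE ratio | 50 sites, planned | 50 sites, site-clustered |
|---|---|---|---|---|---|
| 0 | 0.946 | 0.942 | 0.99 | 0.948 | 0.936 |
| 0.3 | 0.926 | 0.944 | 1.09 | 0.908 | 0.946 |
| 0.6 | 0.882 | 0.930 | 1.18 | 0.856 | 0.920 |
| 1.0 | 0.859 | 0.932 | 1.29 | 0.804 | 0.925 |

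With ρy = 0 the planned interval covers 0.94 to 0.96. With ρx = 0 it covers 0.94 to 0.95 even at ρy = 0.10. Both kinds of clustering are therefore needed for harm.

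A second simulation used 400 v 400 women, 90 sites, 15% risk, ρy = 0.05 and 1500 runs. The nominal 5% error became 4.5%, 7.9%, 10.8% and 13.6% at ρx = 0, 0.3, 0.6 and 1. The formula agrees: m = 8.89 gives DE = 1.41 and 1.68 at ρx = 0.6 and 1, that is, errors of about 10% and 13%.

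**Step 3: Cox model.** The SAP names no variance, so a model-based standard error is assumed. Setting: 900 women, 60 sites, 1000 runs per cell. Coverage at ρx = 0, 0.3, 0.6 and 1.0:

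- frailty variance 0.2: 0.95, 0.92, 0.90, 0.87
- frailty variance 0.5: 0.94, 0.90, 0.84, 0.77

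**Not covered:** the 6.4.2 rate difference was not simulated. Neither propensity-score matching nor dependence within pairs was modelled, so the figures describe unmatched data.

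**The case against.** The strongest reply is that the decisive condition is not documented. Nothing in either document shows that procedures concentrate by site, and Protocol 7.2 has eligible women seeking either procedure invited to enrol. With an even mix the planned intervals are sound. This stands, and it makes the point conditional. The plan does not rule the condition out, however, and physician-dependent choice makes some concentration plausible.

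A reader might infer that every between-arm interval and p-value is wrong. The documents do not support that. Only 6.4.1 and 6.4.2 state between-arm intervals for the endpoints. In 6.4.4 independence can be inferred only from silence, and the covariate list is open. The Greenwood intervals in 6.4.3 belong to the survival curves. The only between-arm p-values with a named test are for baseline balance (6.1.1).

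A reader might also infer that site physicians determine all the main endpoints. Hypersensitivity and autoimmune events are finally decided by an adjudication committee, and surgery is taken from listed eCRF terms (SAP 6.4). Even for pain and bleeding there are preset triggers, investigator training, a fixed term list and, for chronic pain, a 182-day rule. These measures reduce variation between sites but do not exclude it.

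Nor is region the only nearby covariate. The Table 1 physician characteristics may enter the propensity score and describe procedure experience directly. They do not identify the site and do not change the variance formula.

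Finally, the plan already calls itself exploratory and concedes confounding that analysis cannot overcome. That limits the weight of any error rate, but conceding bias does not make an interval formula valid.

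**Conclusion.** The point holds conditionally. No planned analysis accounts for site, and the two stated between-arm intervals carry their nominal 95% only if women are effectively independent or procedures are evenly mixed within sites. The concern is greatest for pain and bleeding and weaker for the adjudicated endpoints and surgery, where sites may still influence referral, capture and surgical practice.

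The size cannot be established from the documents. Over the assumed range it runs from negligible to severe, and the central figures depend on an outcome ICC of 0.05 that the documents neither give nor exclude. It would be wrong to read those figures as the actual coverage of this study, or as results for the matched primary set.

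It would also be wrong to read the point as being about variance alone. If sites differ in both recording and procedure mix, the estimate itself is confounded by site, and a wider interval leaves that bias in place. The change is worth making because it is cheap and has little effect on the intervals if the condition does not arise.

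**What to change.** In SAP 6.4.1, 6.4.2 and 6.4.4, or at least as a prespecified sensitivity analysis in 6.8:

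- Report between-group 95% intervals for the main endpoints with variance clustered on study site and a small-sample correction. The correction is needed because simple clustered intervals covered only about 0.92 to 0.95 in the simulation above.
- In the adjusted sets, use a two-way variance (matched pair and site), since pairs can cross sites and clustering on a single identifier is not enough. A bootstrap that resamples sites is an alternative; state whether matching is repeated in each resample.
- Tabulate the Essure to laparoscopic mix by site.
- Add one supportive Cox model stratified by site for the main endpoints, to address site confounding.

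The cost is SAP wording and modest programming. The first five digits of the subject number identify the center (Protocol 6.5), so no new data are needed. Intervals will widen where procedures concentrate by site: by a factor of 1.09 to 1.29 in standard error for 900 women at 90 sites with outcome ICC 0.05. The stratified model draws only on sites that performed both procedures, so it may be imprecise.

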#### **6.4.5 Procedure failures that are converted to alternative permanent sterilizations**

A conversion is defined as the change of treatment agent from Essure to laparoscopic tubal sterilization. It is also possible that a subject may convert from an unsuccessful laparoscopic tubal sterilization to Essure.

Subjects will be analyzed according to the group based on the initial index event. All the variables will be summarized from subjects' enrollment till end of study or censoring date. The subjects will be followed for safety monitoring until the end of study no matter if the subjects had attempted alternate permanent sterilization procedure or not.

#### **6.4.6 Reporting of longitudinal data**

Analysis of longitudinal data (e.g., PRO data) will be descriptive.

### **6.5 Additional safety analysis**

In addition to the analysis of the main outcomes (safety variables as described in Section 6.3), the following additional safety analyses will be performed.

#### **6.5.1 Adverse events**

The subject incidence overall and by MedDRA preferred term within the primary system organ class (SOC) will be shown for the following events:

1. any treatment-emergent AE
2. any treatment-emergent serious AE
3. any study procedure-related treatment-emergent AE (also by specific procedures/devices: related to hysteroscopy, Essure placement, laparoscopy, cauterization/thermal device, Essure insert, clip or ring placement, trochar or veress needle, anesthesia, TVU, HSG, other)
4. any serious study procedure-related treatment-emergent AE (also by specific procedures/devices: related to hysteroscopy, Essure placement, laparoscopy, cauterization/thermal device, Essure insert, clip or ring placement, trochar or veress needle, anesthesia, TVU, HSG, other)
5. any treatment-emergent bleeding event (as reported by investigator)
6. any study procedure-related treatment-emergent bleeding event (as reported by investigator) (also by specific procedures/devices: related to hysteroscopy, Essure placement, laparoscopy, cauterization/thermal device, Essure insert, clip or ring placement, trochar or veress needle, anesthesia, TVU, HSG, other)
7. any treatment-emergent serious bleeding event (as reported by investigator)
8. any treatment-emergent serious study procedure-related bleeding event (as reported by investigator) (also by specific procedures/devices: related to hysteroscopy, Essure placement, laparoscopy, cauterization/thermal device, Essure insert, clip or ring placement, trochar or veress needle, anesthesia, TVU, HSG, other)

9. any treatment-emergent pelvic/abdominal pain event, including both chronic and non-chronic (as reported by investigator)
10. any study procedure-related treatment-emergent pelvic/abdominal pain event, including both chronic and non-chronic (as reported by investigator) (also by specific procedures/devices: related to hysteroscopy, Essure placement, laparoscopy, cauterization/thermal device, Essure insert, clip or ring placement, trochar or veress needle, anesthesia, TVU, HSG, other)
11. any treatment-emergent serious pelvic/abdominal pain event, including both chronic and non-chronic (as reported by investigator)
12. any treatment-emergent serious study procedure-related pelvic/abdominal pain event, including both chronic and non-chronic (as reported by investigator) (also by specific procedures/devices: related to hysteroscopy, Essure placement, laparoscopy, cauterization/thermal device, Essure insert, clip or ring placement, trochar or veress needle, anesthesia, TVU, HSG, other)
13. any treatment-emergent AE excluding bleeding and pelvic/abdominal pain events (as reported by investigator)
14. any study procedure-related treatment-emergent AE excluding bleeding and pelvic/abdominal pain events (as reported by investigator) (also by specific procedures/devices: related to hysteroscopy, Essure placement, laparoscopy, cauterization/thermal device, Essure insert, clip or ring placement, trochar or veress needle, anesthesia, TVU, HSG, other)
15. any treatment-emergent serious AE excluding bleeding and pelvic/abdominal pain events (as reported by investigator)
16. any treatment-emergent serious study procedure-related excluding bleeding and pelvic/abdominal pain events (as reported by investigator) (also by specific procedures/devices: related to hysteroscopy, Essure placement, laparoscopy, cauterization/thermal device, Essure insert, clip or ring placement, trochar or veress needle, anesthesia, TVU, HSG, other)
17. any treatment-emergent AE leading to discontinuation
18. any treatment-emergent AE leading to (prolonged) hospitalization
19. any treatment-emergent AE of special interest (identified via a list of pre-specified standardized MedDRA queries)
20. any treatment-emergent AE leading to death.

The SOC and the preferred terms within the SOC will be displayed alphabetically. In addition, a summary table for the event types specified above will be prepared that displays the overall number of events and the incidence proportion.

All subjects with AE will be listed with all details from the AE report form as well as corresponding MedDRA PT and SOC. Subjects who died will be listed with type and duration of treatment, administered concomitant medication (incl. indication) as well as details from all reported AEs. For

subjects with bleeding events data listings will be prepared which present all information from the bleeding questionnaire.

Adverse events which occur after the censoring date will be summarized in a separate table. The subjects will be grouped into three groups based on the censoring reason (i.e., ‘Hysterectomy’ [includes any subject with a subtotal, total or radical hysterectomy], ‘Both Treatment’ [includes subjects who attempted both procedures] and ‘Other’ [includes device removal not accompanied by sterilization procedure; or any other censor event not covered by the Hysterectomy or Both Treatments groups]).

### **6.5.1 Device events**

All device events will be coded using MedDRA.

Frequency tables showing an overall summary of the number of device events and the number of subjects with device events by system organ class (SOC) and preferred term (PT) will be given for the following types of device events:

- All Device Events
- Outcome of Device Event (by device)
- Serious AEs (SAEs) related to the Device Event (by device)

